## 2.0

### Abbreviations

Paritaprevir/r	Paritaprevir/ritonavir
AE	adverse event
APRI	AST to platelet ratio index
AFP	alfa fetoprotein
ALT	alanine-aminotransferase
AST	aspartate-aminotransferase
ABBVIE	Paritaprevir/r – ombitasvir ± dasabuvir
REGIMEN	
ANCOVA	analysis of covariance
BMI	body mass index
BMQ	beliefs medication questionnaire
CA	competent authority
CD4	cluster of differentiation 4
CHC	chronic hepatitis C
CI	confidence interval
CNI	calcineurin
CP	core population
CPFSU	core population with sufficient follow-up data
CT	computer tomography
DAA	direct-acting antiviral agent
DDI	drug-drug interaction
EC	ethics committee
EDC	electronic data capture
eCRF	electronic case report form
EMA	European Medicines Agency
EoT	end of treatment
FDA	Food and Drug Administration

---

Confidential Information

No use or disclose outside AbbVie is permitted without prior written authorization from AbbVie

Core Protocol Version 3.0 – Belgium Version 2.0 (9 June 2015)

Page 5 of 58

---

FIB-4	Fibrosis-4 Score/Index
γ-GT	gamma-glutamyltransferase
HCC	hepatocellular carcinoma
HCP	health care provider
Hb	hemoglobin
HbA1c	hemoglobin A1c
HBV	hepatitis B virus
HCV	hepatitis C virus
HDL	high-density lipoprotein
HIV	human immunodeficiency virus
HOMA	homeostasis model assessment
HVPG	hepatic venous pressure gradient
ICMJE	International Committee of Medical Journal Editors
IEC/IRB	independent ethics committee/- review board
IgA	Immunoglobulin A
IgG	Immunoglobulin G
IgM	Immunoglobulin M
INN	international non-proprietary name
INR	international normalized ratio
LDL	low-density lipoprotein
LLoD	lower limit of detection
LLoQ	lower limit of quantification
MAH	Marketing Authorization Holder
MedDRA	Medical Dictionary for Regulatory Activities
MLR	multiple logistic regression
MRI	magnetic resonance imaging
NCP	non-core population
NS3/NS4A	nonstructural protein 3/nonstructural protein 4A
NS5A	nonstructural protein 5A

---

Confidential Information

No use or disclose outside AbbVie is permitted without prior written authorization from AbbVie

---

NS5B	nonstructural protein 5B
OATP	organic anion-transporting polypeptide
OLT	orthotopic liver transplant
PAM-13	Patient Activation Measure 13
PCR	polymerase chain reaction
pegIFN	pegylated interferon
PRO	patient reported outcome
PSP	patient support program
PT	preferred term
RBV	ribavirin
RF	rheumatoid factor
RNA	ribonucleic acid
SAE	serious adverse event
SAP	statistical analysis plan
SD	standard deviation
SDP	study designated physician
SNP	single nucleotide polymorphism
SOC	system organ class
SP	safety population
SVR	sustained virological response
SVR12	SVR at 12 weeks after EoT
SVR24	SVR at 24 weeks after EoT
TAI	total activity impairment
TP	target population
TWP	total work productivity impairment
VAS	visual analogue scale
WHO	World Health Organization

## 4.0 Abstract

**Title:**

Real World Evidence of the Effectiveness of Paritaprevir/r – Ombitasvir, ± Dasabuvir, ± Ribavirin in Patients with Chronic Hepatitis C  
An Observational Study in Belgium.

**Rationale and Background:**

The interferon-free combination regimen of Paritaprevir/r – ombitasvir with or without dasabuvir (ABBVIE REGIMEN) ± ribavirin (RBV) for the treatment of chronic hepatitis C (CHC) has been shown to be safe and effective in randomized controlled clinical trials with strict inclusion and exclusion criteria under well controlled conditions.

The ABBVIE REGIMEN is expected to be first available in Belgium for the treatment of CHC in 2015.

The rationale for this observational study is to determine how the efficacy and safety of the ABBVIE REGIMEN as demonstrated in pivotal trials translates into real world everyday clinical settings, which means evaluating its effectiveness. Whereas efficacy can be defined as a measure of the capacity of a treatment to produce the desired effect in a controlled environment, such as in a randomized controlled trial, effectiveness is the extent to which a drug achieves its intended effect in the usual clinical setting. Effectiveness trials typically have limited exclusion criteria and will involve the broader patient populations in routine clinical practice and per local label which might include patients with heterogeneous compliance patterns and patients with significant comorbid conditions and could be used to model and disseminate best practices. Effectiveness research allows for external patient-, provider-, and system-level factors and can therefore be more relevant for health-care decisions by both providers in practice and policy-makers.

This observational study is the first effectiveness research examining the ABBVIE REGIMEN ± RBV, used according to local label, under real world conditions in Belgium in a clinical practice patient population.

During the last decade when dual therapy with pegylated interferon (pegIFN) plus RBV was standard of care for the treatment of CHC, the discovery of predictive factors for virological response and the subsequent development of treatment algorithms marked a milestone in patient care for CHC. As a consequence, treatment could be effectively targeted to patients most likely to respond. Interestingly, many of the now well established predictors of response to pegIFN/RBV and first generation direct acting antivirals (DAAAs) in combination with pegIFN/RBV were not predictive of outcome in the development trials of the ABBVIE REGIMEN ± RBV. This observational study may play an important part in bridging the data gaps. It may help identify predictive factors of response that are important in real world treatment settings and thus, could assist in further optimizing treatment with the interferon-free ABBVIE REGIMEN ± RBV in the future.

The label of the ABBVIE REGIMEN ± RBV will vary according to hepatitis C virus (HCV) genotype/subtype and stage of liver disease. It is therefore relevant to understand the pattern of use and outcome in daily clinical practice. In addition, this study will provide data on the impact of adherence on treatment outcomes in everyday settings, which may help treating physicians

Confidential Information

No use or disclose outside AbbVie is permitted without prior written authorization from AbbVie

to improve the management of patients under their care.

The aim of this observational study is to provide evidence of the effectiveness and of the influence of adherence on treatment outcome of the ABBVIE REGIMEN ± RBV in a real world setting across clinical practice patient populations.

**Research Question and Objectives:**

What is the effectiveness and the influence of adherence on treatment outcome of the interferon-free ABBVIE REGIMEN ± RBV in patients with CHC in a real life setting across clinical practice patient populations?

**Primary Objective**

1. To describe in routine clinical practice the effectiveness of the interferon-free ABBVIE REGIMEN ± RBV in patients with CHC as evidenced by sustained virological response at 12 weeks after end of treatment (SVR12)

**Secondary Objectives**

2. To provide real world evidence for predictive factors of virological response
3. To describe the pattern of real world use of the ABBVIE REGIMEN ± RBV with respect to different patient and treatment characteristics
4. To evaluate the influence of adherence on treatment outcome in routine clinical practice
5. To evaluate the contribution of the patient support program (PSP) to disease control, treatment continuation over time, patient satisfaction and PSP utilization
6. To assess viral resistance patterns

**Study Design:**

This is a prospective, multi-center observational study in patients receiving the interferon-free ABBVIE REGIMEN ± RBV.

The prescription of a treatment regimen is at the discretion of the physician in accordance with local clinical practice and label, is made independently from this observational study and precedes the decision to offer the patient the opportunity to participate in this study.

**Target Population:**

Patients are eligible for observation in this cohort if the following applies:

- Treatment-naïve or -experienced adult male or female patients with confirmed CHC, genotype 1 or 4, receiving combination therapy with the interferon-free ABBVIE REGIMEN ± RBV according to standard of care and in line with the current local label
- If RBV is co-administered with the ABBVIE REGIMEN, it has been prescribed in line with the current local label (with special attention to contraception requirements and contraindication during pregnancy)
- Patients must voluntarily sign and date an informed consent prior to inclusion into the study
- Patient must not be participating or intending to participate in a concurrent interventional therapeutic trial

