## **9.0      Research Methods**

### **9.1      Study Design**

This is a prospective, multi-center observational study in patients receiving the interferon-free ABBVIE REGIMEN with or without RBV. The prescription of a treatment regimen is at the discretion of the physician in accordance with local clinical practice and label, is made independently from this observational study and precedes the decision to offer the patient the opportunity to participate in this study.

Adult patients chronically infected with HCV, receiving the interferon-free ABBVIE REGIMEN will be offered the opportunity to participate in this study during a routine clinical visit at the participating sites.

[figure not shown]
After written informed consent has been obtained, patient data including demographic data, HCV disease characteristics, co-morbidities, co-medication, treatment details, and laboratory assessments as recorded in the patient's medical records (source documentation) will be documented in the electronic case report form (eCRF). Patients will be observed for the duration of the ABBVIE REGIMEN therapy and for up to 24 weeks after treatment completion. No patient identifiable information will be captured, a unique patient number will be automatically allocated by the web based eCRF system once the investigator or designee creates a new patient file.

This study is focusing on collecting real-world data. Follow-up visits, treatment, procedures and diagnostic methods will follow physicians' routine clinical practice. The observational study period entails the following data collection schemes, data documented will be those closest to the time windows as indicated in Figure 1:

- 12-week treatment regimen: four visits plus two interim data collection windows
- 24-week treatment regimen: four visits plus three interim data collection windows

This schedule is based on the anticipated regular follow-up for patients undergoing treatment for CHC.

Figure 1 - Study Flowchart

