**Table 2 - Data Documentation Schedule**

Assessment/ Procedure (only available data to be collected; no diagnostic or monitoring procedures to be applied to the patients apart from those of routine clinical practice)	Baseline	Treatment Period			Post-treatment (PT) Period		
		On-treatment visits	Mid treatment visit for pts receiving 24 weeks of therapy	EoT b	Early PT visit	SVR 12 visit	SVR 24 visit
Informed consent	X a						
Demographic information	X						
IL28B	X						
Relevant CHC disease characteristics	X						
Liver fibrosis stage	X						
CHC treatment history	X						
HCV genotype and subtype	X						
HCV RNA samples	X	X	X	X	X	X	X
Clinical chemistry and hematology	X	X	X	X	X	X	X
ABBVIE REGIMEN initiation documentation	X						
ABBVIE REGIMEN adherence		X	X	X			
Concomitant medication	X	X	X	X			
Relevant medical history, co-morbidities	X						
sAE, AE and pregnancy reporting	X	X	X	X	X c	X d	X d
For patients receiving RBV: Evidence, in accordance with local label, that female patient or female partner of male patient is not pregnant	X						
Data on portal hypertension in patients with cirrhosis	X			X		X	X
Viral resistance sample	X			X		X	X
BMQ, PAM-13	X			X			
PSP evaluation		X	X	X	X	X	

Abbreviations: EoT = End of Treatment (at Week 12 or 24 or at premature discontinuation),  
PT = Post-Treatment

- a Written informed consent must be obtained before any data documentation in the eCRF
- b Patients who prematurely discontinue should return to the site to document EoT data
- c Tolerability documentation until PT week 4
- d Pregnancy reporting for patients treated with DAA plus RBV

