## **11.4 Serious Adverse Event Collection Period**

SAEs will be reported to AbbVie from the time the physician obtains the patient's informed consent until 30 days or 5 half-lives following the intake of the last dose of physician-prescribed treatment.

---

Confidential Information

No use or disclose outside AbbVie is permitted without prior written authorization from AbbVie

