4.2 Statistical and Analytical Methods

4.2.1 Analysis Populations and Analysis Groups

Population of Patients Enrolled [EP]

The population of patients enrolled comprises all patients who voluntarily sign and date an informed consent prior to inclusion into the study and data were captured in the eCRF.

Target Population [TP]

Patients will be included if the following applies:

- Age at least 18 years
- Confirmed CHC with genotype 1 and/or 4 only, receiving combination therapy with the interferon-free ABBVIE REGIMEN \pm RBV. The prescribed ABBVIE REGIMEN needs to be known.
- Have voluntarily signed and dated an informed consent prior to inclusion into the study
- Must not be participating or intending to participate in a concurrent interventional therapeutic trial

Core Population [CP]

The core population is defined as all patients of the target population (TP) (definition see above), who are adequately treated according to the standard of care and within local label recommendations for their specific disease characteristics (cirrhotic status, genotype). The following patients will be excluded from the CP:

- Patients with unknown fibrosis status
- Cirrhotic patients with genotype 1a not receiving ribavirin
- Patients with genotype 1 for whom 2DAA instead of 3DAA is prescribed
- Patients with genotype 4 not receiving RBV

Non-Core Population [NCP]

Patients in the TP who are not in the CP.

Core Population with Sufficient Follow-up [CPSFU {12, 24}]

In addition, the core population with sufficient follow-up data regarding SVR12 or SVR24, respectively, is defined as all CP patients,

- who have evaluable HCV RNA data ≥ 70 days or >126 days, respectively, after the last actual dose of the ABBVIE REGIMEN
- or a HCV RNA value ≥ 50 IU/mL at the last measurement
- or had HCV RNA <50 IU/mL at the last measurement, but no HCV RNA measurement ≥ 70 days or >126 days, respectively, after the last actual dose of the ABBVIE REGIMEN due to reasons related to safety (e.g. dropped out due to adverse event) or virologic failure (e.g. virologic failure such as relapse is reported in the electronic case report form (eCRF) but date and value of the corresponding HCV RNA test is missing).

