4.2.8.3 Adverse Events

All tolerability variables will be summarized using descriptive statistical methods for the SP stratified by treatment regimen and cirrhosis status and overall.

AEs will be coded using MedDRA. A glossary will show the verbatim terms and the corresponding coded terms used (see Table 12).

The number and percentage of patients with treatment-emergent AEs (i.e. any reported event that begins or worsens in severity after initiation of study drug through 30 days post-study drug dosing including those who are related to the study drug independent of the occurrence and those where the date of onset is missing) will be tabulated by primary MedDRA SOC and PT.

Corresponding summary tables will be provided for all serious treatment-emergent AEs and additional for all non-serious treatment-emergent AEs. In the table of non-serious AEs (that must exclude any SAE) only preferred terms that occurred at a frequency of $\geq 5\%$ in any treatment group will be displayed (no SOCs will be displayed).

The tabulation of the number of patients with treatment-emergent AEs by severity (AEs by severity [mild, moderate, severe], AEs leading to death, AEs leading to hospitalization) and relationship to study drug will also be provided (ABBVIE Regimen, ribavirin, medication error - paritaprevir/r-ombitasvir, medication error – dasabuvir, ABBVIE Regimen withdrawn, ribavirin withdrawn).

Patients reporting more than one AE for a given MedDRA PT will be counted only once for that term using the most severe incident for the severity summary table and the most related for the relationship summary table. Patients reporting more than one type of event within a SOC will be counted only once for that SOC.

The frequency of pregnancies will be displayed as well.

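### No visible text limits the time from first dose to consent, so any late entrants can bias SVR12 upward, and their pre-consent SAEs fall outside the reporting period

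*Protocol*

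**What the plan says.** **Who may enter.** The Abstract and protocol 9.2.1 describe eligible patients as "genotype 1 or 4, receiving combination therapy with the interferon-free ABBVIE REGIMEN ± RBV". The target population in SAP 4.2.1 uses the same participle and sets no limit on time since first dose.

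**When they are asked.** The prescribing decision "precedes the decision to offer the patient the opportunity to participate in this study" (Abstract, Study Design). Protocol 9.1 adds that adult patients "receiving the interferon-free ABBVIE REGIMEN will be offered the opportunity to participate in this study during a routine clinical visit". Neither passage ties the invitation to the first dose.

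**Consent.** Patients must "Have voluntarily signed and dated an informed consent prior to inclusion into the study" (SAP 4.2.1). Footnote a of protocol Table 2 says "Written informed consent must be obtained before any data documentation in the eCRF". Consent is therefore tied to inclusion and to data entry, not to treatment start.

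**Analysis sets.** The core population (protocol 9.7.1, SAP 4.2.1) depends on receiving label-concordant treatment. The safety population (SAP 4.2.1) is everyone enrolled who took a dose of a known regimen. Neither compares consent date with first-dose date, and the disposition tables in SAP 4.2.5 do not show the interval.

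**Safety periods.** Protocol 11.4: "SAEs will be reported to AbbVie from the time the physician obtains" informed consent. SAP 4.2.8.3 defines treatment-emergent events as "any reported event that begins or worsens in severity after initiation of study drug", up to 30 days after dosing. Protocol 9.7.6 and 11.5 give no start date for non-serious events.

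**The concern.** A patient consented at week 4 must still have been on treatment and in care at week 4, yet is analysed from study day 1, the first treatment day. Someone who stopped, died or was lost in week 2 can no longer be enrolled that way. Late entrants are therefore a group from which early failures have been removed.

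The rule that counts missing SVR12 as failure (protocol 9.7.1, SAP 4.2.3) does not help, because it reaches only enrolled patients. Any resulting bias in SVR12, completion and adherence is upward. Protocol 9.9 warns only of bias in the other direction, from missing HCV RNA. For a study meant to show how trial results carry over to routine practice, that direction matters.

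On safety, a late entrant sits in the denominator from first dose, but the stated SAE reporting period begins only at consent.

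**Working it through.** **1. The plan's own precision figures.** Exact Clopper-Pearson limits for 417 patients at 90% are 86.71 to 92.71, width 6.00, as in protocol Table 3. The interval reaches 90 − 86.71 = 3.29 points below the estimate and 92.71 − 90 = 2.71 above. Enrolment: 417/0.95 = 438.9, so 439 against the stated 440. These figures stand and are not affected by this point.

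**2. Size of the selection effect.** Let S be SVR12 among all who start treatment, q the share of starters who would be approached only later, and e the share of starters who stop, die or are lost before that later time. Count every early failure as a non-responder, which is the worst case. All responders remain available for enrolment, and a fraction q × e of starters is lost from the denominator:

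observed SVR12 = S / (1 − q × e)

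The documents give neither q nor e. Protocol 7.1 says only that discontinuation in phase III was low. The values below are assumptions. Upward shift in points at S = 90%:

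| | e = 1% | e = 2% | e = 4% |
|---|---|---|---|
| q = 25% | 0.23 | 0.45 | 0.91 |
| q = 50% | 0.45 | 0.91 | 1.84 |
| q = 75% | 0.68 | 1.37 | 2.78 |

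Examples: 0.90/(1 − 0.50 × 0.02) = 0.90/0.99 = 90.91%; 0.90/(1 − 0.75 × 0.04) = 0.90/0.97 = 92.78%. At S = 95% the corners are 0.24 and 2.94 points.

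Defining the late share among enrolled patients (f) instead gives nearly the same answer: 0.5 × 90 + 0.5 × 90/0.98 = 90.92 at f = 50%, e = 2%. If nobody enters late, the shift is zero.

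**3. SAE window.** For a 12-week course the treatment-emergent window is 84 + 30 = 114 days. Consent at day 14 leaves 14/114 = 12% of it before SAE reporting starts; consent at day 28 leaves 28/114 = 25%.

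**4. Can late entry happen under the text?** Four provisions leave it open:
- eligibility rests on receiving treatment;
- only available data are collected (protocol Table 2);
- baseline laboratory values are the last on or before day 1 and can come from the chart (protocol Table 4);
- the 36 and 48 weeks of observation in protocol 9.2.2 are maxima.

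**The case against.** The strongest reply is that the plan plainly expects entry at or before treatment start. Observation runs from the baseline visit (protocol 9.2.2). Portal hypertension is to be assessed before treatment begins (9.3.2). PAM-13, BMQ and a resistance sample are baseline items (9.4.1.1, Table 2), and the questionnaires cannot be filled in from a chart. SAP 4.2.5 lists never having started treatment as a reason for not completing the study, so enrolment before dosing is foreseen. Figure 1, the study flowchart, was not reproduced in the copy reviewed and may place inclusion relative to first dose. All of this stands as evidence of intent. It makes frequent late entry less likely, but none of the visible text excludes it.

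A reader might go further in four ways that the documents do not support.

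- *That SVR12 is raised.* This depends on late entry and early failure both occurring, and the documents quantify neither.
- *That all early adverse events go uncollected.* The text shows this for SAEs only. Non-serious events have no stated start, data are transcribed from medical records, and SAP 4.2.8.3 counts even events with a missing onset date.
- *That the week-1 bilirubin peak described in protocol 7.1 is lost through late entry.* The first on-treatment laboratory window opens at day 15 (protocol Table 4, SAP Table 4), and bilirubin is in neither SAP Table 10 nor Table 11. A week-1 value has no on-treatment visit window even for a patient enrolled on day 1.
- *That the primary analysis should move to patients consented by day 1, or that consent by day 1 should become a hard entry rule.* In a non-interventional study this is debatable. If 25% to 75% of the 440 enrolled were late, 330 to 110 would remain (440 × 0.75; 440 × 0.25), short of the 417 evaluable patients planned.

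**Conclusion.** The gap is real and cheap to close. Visible text in both documents permits enrolment after first dose, sets no limit on the interval and would not report it.

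If late entry occurs, the expected bias in SVR12, completion and adherence is upward. Its size cannot be derived from the documents. At a true rate of 90% it is under 1 point when early failure is 2% or less and no more than half are approached late, and about 2.8 points at 4% and 75%. These values rest wholly on assumed rates and on counting every early failure as a non-responder. In the moderate cases the shift is smaller than the planned interval's reach of 2.7 to 3.3 points, but it is systematic, so a larger sample does not shrink it.

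The mismatch between the SAE reporting period and the treatment-emergent window needs no assumption about rates. It is in the text, and it affects any patient consented after first dose.

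**What to change.** - **SAP 4.2.1 and 4.2.5:** derive days from first dose to consent. Report the distribution, and the number consented after study day 1, in the disposition tables.
- **SAP 4.2.7.1 and 4.2.8.3:** keep the core-population primary analysis. Add a prespecified sensitivity analysis that repeats SVR12 and the treatment-emergent AE and SAE tables in patients consented on or before study day 1.
- **Protocol 9.2.1:** state the intended timing of consent relative to first dose. If Figure 1 already shows it, repeat it in the text.
- **Protocol 11.4:** align the start of SAE collection with the treatment-emergent window, for example by entering pre-consent on-treatment SAEs from the chart, or state the limitation in 9.9.

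**Cost.** A derived variable, a few extra tables, and a smaller sensitivity set with a wider interval. SVR12 in that set may look slightly less favourable. Consent forms are dated and the first dose is documented (protocol 9.3.2), but protocol 9.4.1.1 does not list the consent date as an eCRF item. If it is not captured, it must be taken from the forms. The enrolment target does not change. If nobody entered late, the disposition table will show it.
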